## 2. SYNOPSIS

NAME OF SPONSOR: Spyryx Biosciences, Inc.	PROTOCOL No.: SPX-101-CF-201
NAME OF STUDY TREATMENT: SPX-101 Inhalation Solution	
TITLE OF STUDY: A Randomized, Double-Blind, Placebo-Controlled Phase II Study to Evaluate the Efficacy and Safety of SPX-101 Inhalation Solution in Subjects with Cystic Fibrosis (HOPE-1 Study: Hydration for Optimal Pulmonary Effectiveness )	
STUDY CENTERS: Approximately 25 centers are planned internationally	
STUDY PERIOD: After a 3- to 28-day screening period, enrolled subjects will be in the study for approximately 30 days.	PHASE OF DEVELOPMENT: Phase II
PLANNED STUDY DATES: The study is expected to start in Q3 2017 and conclude in 2019	
OBJECTIVES:	
Primary Objective: 
 
To evaluate the efficacy of SPX-101 in subjects with cystic fibrosis (CF)
 
	
Safety Objectives: 
 
To evaluate the safety and tolerability of SPX-101 in subjects with CF
 
	
Pharmacokinetic Objective: 
 
To assess the extent of systemic exposure of SPX-101 in a subset of subjects
 
	
STUDY DESIGN AND METHODOLOGY:	

This randomized, double-blind, placebo-controlled, Phase II study is designed to evaluate the efficacy and safety of SPX-101 inhalation solution, administered in different dose regimens, in a 28-day treatment period in approximately 90 adults with CF. Two sequential cohorts are planned to compare the study drug SPX-101 with placebo. Each cohort will have its own baseline and will be analyzed separately.
	

Cohort 1
 
In Cohort 1, 46 subjects were randomized in a 1:1:1 ratio to 3 groups (2 treatment groups and 1 placebo group); to achieve balance between treatment groups, randomization was stratified by baseline lung function (percent predicted forced expiratory volume in 1 second [ppFEV1] 40.0% to 55.0% or 55.1% to 80.0%). Cohort 1 treatment groups were the following:
 
 
Placebo twice daily (BID) x 28 days
 
SPX-101 60 mg BID x 28 days
 
SPX-101 120 mg BID x 28 days
 
	

Cohort 2
 
In Cohort 2, approximately 45 subjects will be randomized in a 2:1 ratio to either SPX-101 120 mg BID or placebo BID. Subjects will be stratified according to concomitant hypertonic saline use, so that approximately 50% will be using hypertonic saline (defined as having used a constant regimen for 28 days prior to screening and planning to continue their usual concentration without change for 28 days post-randomization). The decision to use 120 mg BID in Cohort 2 was based on the relatively greater improvements in the lung function at that dose in Cohort 1, and a need to define the variability in response within the population.
 
For each cohort, there will be 5 clinic visits and 2 telephone calls: Visit 1 (Screening; Day -28 to Day -3); Visit 2 (Randomization; Day 1); Visit 3 (Day 8 -1); Visit 4 (Day 15 -2/+1); telephone
	

call (Day 22 ± 3); Visit 5 (Day 29 ± 2; end-of-treatment); and a follow-up telephone call 2 days later (Day 31 ± 1; end-of-study). All study visits for an individual subject will be scheduled at approximately the same time of day to minimize the confounding effects of diurnal variation in lung function, background therapies, and daily chest physiotherapy regimens. Subjects will be screened at Visit 1 and then will enter a variable-length screening period of 3 to 28 days, to time the randomization so that the first dose of the investigational product will coincide, if applicable, to the first day of an inhaled antibiotic cycle. In Cohort 1, subjects who still met the randomization criteria on Day 1 (Visit 2) were randomized to 1 of the 3 treatment groups. In Cohort 2 subjects who still meet the randomization criteria on Day 1 (Visit 2) will be randomized either to the treatment or placebo group, as described.

At Visits 2, 3, and 4, after completing spirometry and other assessments, subjects will self-administer the study medication in the clinic. On Day 1 (Visit 2) only, subjects will be monitored for safety for the first 4 hours after completion of administration of the study drug. Monitoring will include spirometry, vital signs, and adverse event (AE) assessments as described in more detail in the protocol. After the 4-hour postdose assessments are complete, subjects who have tolerated the study medication will be discharged with a sufficient supply of medication to take BID on an outpatient basis until their next clinic visit.

Subjects who regularly use a short-acting β-agonist (SABA) should administer this medication at least 4 hours before spirometry on clinic days, and they should use the SABA consistently throughout the study.

#### **STUDY POPULATION AND MAIN CRITERIA FOR INCLUSION/EXCLUSION:**

Subjects cannot be enrolled or randomized before all inclusion criteria (including test results) are confirmed. A subject may be re-screened once if they fail to meet randomization criteria for any reason. If this is the case, a new consent form must be signed, and a new screening number will be used.

#### **Inclusion Criteria:**

1. Ability to provide written, personally signed, and dated informed consent to participate in the study, in accordance with the ICH GCP Guideline E6 and applicable regulations, before completing any study-related procedures
2. Ability and willingness (in the judgment of the Investigator) to attend study visits and fully comply with study procedures and restrictions; study visits will occur at approximately the same time of day throughout the study and under specified conditions with respect to daily respiratory clearance and medication regimens
3. Ability to self-administer the investigational product
4. Male or nonpregnant, nonlactating female subjects aged 18 to 50 years inclusive
5. Diagnosis of cystic fibrosis as determined by the 2008 Cystic Fibrosis Foundation Consensus Guidelines for Diagnosis [1] defined as the presence of signs and symptoms of CF in conjunction with at least 1 of the following:
  - a. Documented sweat chloride test ≥ 60 mEq/L by quantitative pilocarpine iontophoresis
  - b. Two well-characterized, disease-causing genetic mutations in the CF transmembrane conductance regulator (CFTR) gene; the original documentation of genetic testing is not required if the specific mutations are documented in the subject's medical record
6. ppFEV1 as follows:

- a. Cohort 1: between 40.0% and 80.0%
- b. Cohort 2: between 50.0% and 80.0%

Note: spirometry must be performed in accordance with American Thoracic Society/European Respiratory Society end-of-test criteria and the Global Lung Initiative predicted values [2, 3]

- 7. Stable CF lung disease, defined as no pulmonary exacerbation or acute upper or lower respiratory illness other than CF within 28 days preceding screening, except for allergic or nonallergic rhinitis; in addition, subjects may not have had any of the following:
  - a. Significant hemoptysis (at the discretion of the Investigator) within 28 days of screening
  - b. Pneumothorax within 28 days of screening
  - c. Diagnosis of active allergic bronchopulmonary aspergillosis (at the discretion of the Investigator)
  - d. Documented colonization with *Burkholderia cenocepacia* or *Mycobacterium abscessus* within 6 months prior to screening; subjects with other infections in the *Burkholderia* or *Mycobacterium* genii are allowed at the discretion of the Investigator
- 8. No significant changes (removal or addition of medications) to inhaled or oral CF medication regimen within 28 days preceding screening, and no anticipation of need to change this regimen during study participation; short courses of medications used to address an ongoing medical problem are allowed, provided the last dose of such medication was taken > 28 days before screening; subjects for whom a significant change in medication is anticipated during the study will be excluded. Specific requirements for ongoing concomitant medications are below:
  - a. Inhaled antibiotic use: stable antibiotic medication, defined as at least 2 complete 28-day cycles of intermittent monotherapy (if alternating month on and month off with a single inhaled antibiotic) or 2 full cycles if continuous alternating every 28 days between 2 inhaled antibiotics
  - b. Dornase alfa: stable use of daily or intermittent dosing for at least 28 days before screening
  - c. Inhaled bronchodilators: stable dose for at least 28 days before screening
  - d. Inhaled hypertonic saline: stable dose for at least 28 days before screening
- 9. Other concomitant medications may be taken during the study, provided the dose and regimen have been stable for at least 14 days before screening, and the regimen is expected to remain stable during the study
- 10. Stable chest physiotherapy and clearance techniques for at least 28 days before screening, including chest percussion, use of vibrating vests, etc
- 11. All female subjects of childbearing potential must be using a highly effective method of contraception through the duration of the study as follows:
  - a. Female subjects of childbearing potential must not be pregnant, breastfeeding, or attempting to become pregnant for 28 days before screening, throughout the duration of the study, and for 28 days after the last study visit. Subjects must have a negative serum pregnancy test at screening, a negative urine pregnancy test at randomization, and be willing to commit to using a consistent and

acceptable method of contraception for at least 28 days before screening and for the duration of the study, if they are (or become) sexually active. Female subjects of childbearing potential must meet at least 1 of the following:

- i. Consistent use of systemic contraception, including birth control pills, transdermal patch, vaginal ring, implants, and injectables
- ii. Consistent use of double barrier method, eg, condoms, cervical cap, diaphragm, vaginal contraceptive film with spermicide
- iii. Use of intrauterine device with a low failure rate (defined as < 1% risk of pregnancy per year)
- iv. Monogamous intercourse with a vasectomized man or has only same-sex partners
- v. Female subjects who are not sexually active but become so during the study must agree to follow the contraceptive requirements above

b. Female subjects who are not of childbearing potential must meet at least 1 of the following criteria:

- i. At least 1 year since the last menstrual period
- ii. Surgically sterile (tubal ligation, bilateral oophorectomy, salpingectomy, or hysterectomy)
- iii. Congenitally sterile
- iv. Diagnosed as infertile and not undergoing treatment to reverse infertility

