## 9.3 Study Duration

Subjects will enter a screening period of up to 28 days before randomization. Randomized subjects will be in the study for 28 days, with a follow-up phone call approximately 2 days later. The end of the study is defined as the date of the last data recorded, eg, the follow-up phone call at Day 31 or an unscheduled phone call, whichever is later.

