## 12. SAFETY MEASUREMENTS AND VARIABLES

### 12.1 Adverse Events

The definitions and reporting procedures provided in this protocol comply with the current CFR 21 Part 312. An AE is any untoward medical occurrence or worsening of a pre-existing condition, regardless of its relationship to the investigational medicinal product. An AE can therefore be any unfavorable or unintended sign, including an abnormal laboratory finding, symptom, or disease temporally associated with the use of an investigational medicinal product whether or not considered related to the product. Adverse events that are reported after signing the informed consent but prior to randomization, will be recorded in medical history. Adverse events that are reported after initiation of treatment up until the final study visit phone call on Day 31 will be considered TEAEs. Serious adverse events occurring at any time from informed consent to 28 days after the last dose of treatment with study drug will be reported. Subjects will be monitored for AEs throughout the entire study.

Investigators will ask the subject at each visit if they have experienced any untoward effects since the last study visit. The Investigator or designee will record the following information about AEs on the eCRFs: an AE term or description of the event, severity, event start date, event end date (if known), any action (eg, treatment and follow-up tests), the outcome of the event, and the Investigator's assessment of the relationship to the study treatment.

Even if the Investigator feels there is no relationship to the study drug, all AEs must be recorded in the eCRF.

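### Inclusion criterion 11a bars pregnancy until 28 days after the last study visit, but the contraception commitment stops at the end of the study, nominally 26 days earlier

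*Protocol*

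**What the plan says.** Inclusion criterion 11 appears twice in the Protocol, in the synopsis (Section 2) and in Section 9.4.1, with the same periods in both.

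- **Pregnancy bar (11a).** For women who could conceive, the first sentence rules out pregnancy, breastfeeding and "attempting to become pregnant for 28 days before screening, throughout the duration of the study, and for 28 days after the last study visit".
- **Contraception commitment (11a, next sentence).** She must be willing to use a consistent and "acceptable method of contraception for at least 28 days before screening and for the duration of the study", if she is or becomes sexually active.
- **Lead-in to criterion 11.** Women of childbearing potential "must be using a highly effective method of contraception through the duration of the study as follows".
- **Item 11a.v.** "Female subjects who are not sexually active but become so during the study must agree to follow the contraceptive requirements above".

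Items 11a.i to 11a.iv list the accepted methods and set no later end date.

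The end of the study is defined. The synopsis schedule gives Visit 5 at Day 29 ± 2, "and a follow-up telephone call 2 days later (Day 31 ± 1; end-of-study"). Section 9.3 takes the date of the last data recorded and gives as examples "the follow-up phone call at Day 31 or an unscheduled phone call, whichever is later".

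Section 12.1 adds two related periods. Adverse events are treatment-emergent "up until the final study visit phone call on Day 31 will be considered TEAEs", and serious adverse events occurring at any time "from informed consent to 28 days after the last dose of treatment with study drug will be reported".

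**The concern.** The two sentences of 11a start at the same point, 28 days before screening, and end at different ones. The pregnancy bar has a 28-day tail after the last study visit; the contraception commitment has none. Because 11a names the study period and the 28-day tail as separate items, the study period cannot easily be read as including the tail.

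During the study the protocol does not rely on the pregnancy bar alone but adds a contraception requirement. After the Day 31 call only the bar remains. Not attempting to conceive says nothing about unintended conception, and not being pregnant is an outcome rather than an instruction. Item 11a.v has the same limit: a woman who first becomes sexually active after the study ends is outside its wording.

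Nothing scheduled later fills the gap. The last pregnancy test is at Visit 5 (Table 2, Sections 10.6 and 11.2), and the last planned contact is the Day 31 call (Section 10.7).

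What is at stake is an inconsistent safety rule. A participant could follow the contraception wording exactly, stop after the Day 31 call, and have nearly four weeks left in which she must not be pregnant.

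**Working it through.** The documents give no figure for this gap, so there is none to reproduce. The check is day arithmetic.

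**Inputs**

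- Last clinic visit: Visit 5, Day 29 ± 2, so Day 27 to 31 (synopsis, Section 10.6).
- End of study for a subject on schedule: follow-up call, Day 31 ± 1, so Day 30 to 32 (synopsis, Section 10.7).
- Tail of the pregnancy bar: 28 days after the last study visit (criterion 11a).
- Tail of the contraception commitment: none after the end of study (criterion 11 lead-in and 11a).

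**Formula**

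Gap = (Visit 5 day + 28) − call day.

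**Nominal schedule**

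(29 + 28) − 31 = 57 − 31 = **26 days**.

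**Over the permitted windows**, with the call on a later day than Visit 5:

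| Visit 5 day | Bar ends | Call Day 30 | Call Day 31 | Call Day 32 |
|---|---|---|---|---|
| 27 | 55 | 25 | 24 | 23 |
| 28 | 56 | 26 | 25 | 24 |
| 29 | 57 | 27 | 26 | 25 |
| 30 | 58 | – | 27 | 26 |
| 31 | 59 | – | – | 27 |

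The range is **23 to 27 days**. If the call is exactly 2 days after Visit 5, as the synopsis describes, the gap is always 28 − 2 = 26 days.

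**Other readings**

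- The Day 31 call counts as the last study visit (Section 12.1 comes close to calling it one): (31 + 28) − 31 = 28 days.
- Early termination, with the termination visit as the last recorded data: both periods are counted from the same day, so the gap is the full 28 days.
- Call on the same day as Visit 5: 28 days.
- A later unscheduled call moves the end of study under Section 9.3 and shortens the gap one day for each day of delay.

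For a subject on schedule without a later unscheduled call, more than three weeks are uncovered on every reading.

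**Comparison with the last dose**

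No study drug is given at Visit 5 (Section 10.6), and the morning dose is not taken at home on clinic days (Section 9.5.7). The last dose is therefore nominally on Day 28. The contraception commitment lasts 31 − 28 = 3 days beyond it; serious adverse events are reported until Day 28 + 28 = 56, one day before the pregnancy bar ends on Day 57.

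**After the change**

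If contraception also runs to 28 days after the last study visit, both obligations end together, on Day 57 nominally (Day 55 to 59 over the Visit 5 window), and the gap is 0. If the Day 31 call is the last study visit, both end on Day 59 and the gap is again 0.

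**The case against.** The strongest reply is that the post-study period is already regulated. The bar on pregnancy and on attempting it continues, and nothing says contraception may stop. On this view the outcome is stated and only the means is not repeated. It is true that the bar persists, but it does not cover unintended conception, which is what the contraception sentence is for.

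Second, systemic exposure looks very low. Section 7.2.4 reports no measurable plasma concentrations in the 14-day multiple-dose part, up to 120 mg twice daily. In the single-dose part, drug was detected only at 240 mg, in 4 of 6 subjects and only 5 minutes after dosing. That dose is twice the largest single dose in this trial. This stands, and it limits the weight of the point: the documents identify no residual exposure between Day 31 and Day 57. They also do not quantify fetal risk, and the 28-day precaution is the sponsor's own choice.

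Third, Section 12.6 requires a subject who becomes pregnant after exposure to report it and requires follow-up of the pregnancy. That is a reporting safeguard, which helps after conception but does not prevent it.

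Fourth, the appendices on consent elements and subject information are not in the available text and may contain contraception instructions. This cannot be checked. If they do extend contraception, participants may already be told the right thing, but the criterion that sites apply would then disagree with it.

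Finally, the two periods could be aligned by shortening the pregnancy bar, and the serious-adverse-event period does not settle the intended end date because it is counted from the last dose. Both observations are fair. Shortening, however, would drop a stated precaution, and the documents give no rationale for doing so.

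**Conclusion.** The concern holds. Criterion 11a, in both copies, ends the explicit contraception commitment nominally 26 days before the end of the pregnancy bar, or 23 to 27 days before it over the permitted windows. Those figures assume that the last study visit is Visit 5, that the call falls on a later day, that the subject completes on schedule, and that no later unscheduled call occurs. Counting the Day 31 call as the last visit, or early termination with no later data, makes the gap 28 days.

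This is an inconsistency in a participant-safety rule, not evidence of harm. It has no bearing on the primary endpoint, the power or the analysis. The conclusion concerns the eligibility wording; what the consent and subject-information pages say is unknown. It should be corrected because the correction is cheap.

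**What to change.** In the synopsis and in Section 9.4.1, change three sentences:

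1. Criterion 11 lead-in: require contraception *throughout the study and until 28 days after the last study visit*.
2. Criterion 11a commitment sentence: replace the end point with the same period.
3. Item 11a.v: apply it to women who become sexually active at any time in that same period, not only during the study.

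Both obligations then share one anchor, so they end together whichever contact counts as the last study visit. It would help to state in the same edit whether that is Visit 5 (or the termination visit) or the Day 31 call, since the nominal end date is Day 57 or Day 59 accordingly. Do not close the gap by shortening the pregnancy bar.

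Check that the consent form and subject-information text give the same period.

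**Cost.** Three sentences in two places, plus the consent check and whatever approval Section 16.2 requires for the amendment. Participants would have about four more weeks of required contraception, in a period when they must already not be pregnant. No visit, test or analysis is added.

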**Exclusion Criteria:**

1. BMI < 18 kg/m^2
2. Use of a CFTR corrector or potentiator during the study or within 60 days before screening
3. The presence of significant and unstable comorbidities (based on the Investigator's judgment) within 28 days before screening, including diabetes, significant renal or hepatic disease, significant respiratory disease other than CF, cardiac, neurological, or gastrointestinal disease other than those associated with CF. Subjects with stable co-morbidities associated with CF (such as diabetes) may participate per the Investigator's judgment unless specifically prohibited elsewhere.
4. Subjects with either of the following:
  - a. Hepatic impairment defined by elevation of bilirubin > 2 times the upper limit of normal (ULN) or aspartate aminotransferase, alanine aminotransferase, or alkaline phosphatase > 5 times the ULN
  - b. Chronic hepatitis B and/or C
5. History of malignancy in the previous 5 years; subjects who have been successfully treated for non-melanoma skin cancer, cervical cancer, or prostate cancer within the previous 5 years are allowed to enroll with the approval of the Medical Monitor
6. Administration of another investigational drug within 28 days before screening
7. Administration of a vaccination (including influenza) within 7 days before screening
8. Requirement for supplemental oxygen of more than 2 L/min, and/or noninvasive ventilation for the management of respiratory failure; subjects must have been on a stable regimen for at least 60 days before screening (patients who have been using a stable regimen of oxygen ≤ 2 L/min for at least 60 days before screening are eligible to enroll)
9. Current use of tobacco or tetrahydrocannabinol-containing products, delivered orally, by

vaporizing, or by smoking; or a greater than 10 pack-year history of tobacco use

10. Actively listed for lung transplantation
11. Any history of organ transplantation
12. Hospitalization for a respiratory event or CF-related condition within 28 days before screening or any plans for hospitalization for any reason during the study
13. Current use of > 10 mg/day of prednisone/prednisolone (use of  $\leq$  10 mg/day is acceptable)
14. Use of any of the following antihypertensive medications or combinations containing these medications: diuretics (eg, thiazides, loop diuretics, spironolactone, amiloride), angiotensin-converting enzyme inhibitors, angiotensin receptor blockers, or any other drugs known to affect the serum potassium concentration
15. Hypersensitivity to the study drug or any of its excipients
16. Subjects with significant electrocardiogram (ECG) abnormalities at screening or before the first dose on Day 1, including a QT interval corrected by the Fridericia correction formula ( $\geq$  440 msec in men and  $\geq$  460 msec in women)

